2.1 Selection of doses

Everolimus will be dosed at the once daily dose of 10 mg orally continuously. This is the maximum tolerated dose of the drug when dosed on daily continuous schedule. This dose is also the efficacious anticancer dose approved for the treatment of patients with renal cell cancer. The planned dose of Pasireotide LAR is 60 mg intramuscular injection to be given approximately once every 4 weeks. A company-sponsored phase I study of this combination has already determined the proposed doses of 60mg Pasireotide LAR in combination with everolimus 10 mg once daily, to be safe and tolerable.⁵⁰ The study is currently enrolling more patients into an

expansion cohort to obtain additional safety and toxicity data. The final result of this phase I trial is awaited within the next 6 months in time for any dose adjustment for Pasireotide in the current study.

3 Objectives

3.1 Primary objectives

To determine the Response Rate [(complete response (RR) + partial response (PR)] of everolimus, pasireotide and the combination of both agents in the therapy of radioiodine refractory differentiated and medullary thyroid cancer.

To establish the progression free survival associated with everolimus, pasireotide and the combination of both agents in radioiodine refractory differentiated and medullary thyroid cancer.

3.2 Secondary objectives

To determine the clinical benefit rate (CBR: CR + PR + SD)of everolimus, pasireotide and the combination of both agents when used as the frontline treatment for radioiodine refractory differentiated and medullary thyroid cancer.

Determine the Time to Treatment Failure (TTF) for each arm of the study

Assess the rate of and time to biochemical response using changes in serum concentrations of thyroglobulin, carcinoembryonic antigen (CEA), chromogranin A and calcitonin

To obtain additional safety data regarding concurrent and sequential administration of Everolimus and pasireotide

3.3 Exploratory objectives

Correlate the level of expression of mTOR pathway signaling proteins in archival tumor tissue with the clinical activity of everolimus

Correlate the level of expression of somatostatin receptor expression and IGF1-R in archival tumor tissue with clinical efficacy of Pasireotide

Exploratory analysis of disease response based on histology and FDG PET uptake

4 Study design

This is an open-label, 3-arm, non comparative phase II clinical trial to study the single agent and combined efficacy of pasireotide and everolimus in patients with iodine refractory, differentiated (papillary, follicular and their variants) and medullary thyroid cancer. Patients will be randomly assigned to one of three arms to receive single agent pasireotide, everolimus or the combination of both drugs (Figure 4). Patient randomization will be stratified by histology, (medullary versus non medullary thyroid cancer). In order to explore the optimal schedule of administration,

patients who were initially randomized to the single agent arm will be allowed to receive the second agent at the time of disease progression. Such patients, however, may only proceed with the trial if they achieve disease stabilization or objective response at the end of the first 2 cycles of 2-drug combination and without experiencing any grade ≥ 4 hematologic or grade ≥ 3 non-hematologic toxicities. Everolimus will be administered once daily continuously on days 1 to 28; pasireotide will be administered as a long acting intramuscular depot injection given once every 4 weeks. One cycle will be defined as 4 weeks with response assessment with cross sectional imaging planned for the end of every even numbered cycle. Biochemical response will be assessed using serum-based tumor markers (Thyroglobulin, CEA, calcitonin) specific or informative for the histologic subtype of thyroid cancer. Patients will be evaluated at the end of cycle 1 and cycle 2, and subsequently after every 2 cycles along with restaging scans.

The study design for this Phase II trial is a randomized screening design with multiple arms. A simple winner arm is selected only from the arms shown to be superior to the historical control. Between arms: Eligible patients will be randomly assigned to one of three arms to receive single agent pasireotide, everolimus or the combination of both drugs. Randomization is conducted with a block of 3 patients in order to balance the enrollment in each arm (The first of the 3 patients entered consecutively is randomly assigned to any of the 3 arms; the second patient is randomly assigned to one of the remaining 2 arms and the third patient to the last arm).

Within arms: Within each of the 3 arms, a Simon's 2-stage MinMax design is used. Eighteen evaluable patients will be enrolled into stage I. At least one objective response is required to proceed to stage II accrual of 10 additional patients for a total of 28 patients per arm. At least 3 patients must achieve objective response for the particular treatment arm to be considered worthy of further clinical evaluation in this disease.

Between Arms: Any treatment arm closed to accrual after the first stage interim analysis will be considered an inferior arm and will be excluded from comparison for the winner of trials. The arm with the best overall RR at the end of full enrolment will be adjudged the winner to be considered for further development. In the event of identical RR between the arms or if none of the arms met the RR criterion (less than 3 objective responses after full patient enrolment), the 1-yr PFS rate will be employed to determine a winner. Based on recent clinical trials of targeted agents in similar patient population, 90% of patients were alive at 1 year and median progression free survival ranged between 9 and 18 months.⁸⁻¹⁰ We assume a conservative estimate that only 20% of the patients will be progression free at 1 year if the treatment is ineffective while 50% or more of the patients will be progression free at the same time point with an effective regimen. For this purpose, a 1-year PFS rate of 50% or greater will be considered sufficient activity to justify further evaluation of the treatment in this disease. Assuming a 20% or lower 1-year PFS rate with an inactive regimen and a 50% or greater rate with an active regimen, 28 patients enrolled onto each arm will classify the treatment as having sufficient activity for further evaluation with a probability of 0.95 (power against the alternative hypothesis $p = 0.05$). In this respect, the arm with the highest 1-yr PFS rate will be judged the winner. In the event of a tie between the arms for both the RR and 1-yr PFS rate, the arm with the best profile in terms of safety and tolerability will be considered the overall winner to be selected for further evaluation in this disease. The power calculation for PFS assessment assumes full enrolment of 28 patients

to the treatment arm, therefore any arm closed to further accrual following the initial interim analysis will not be considered for PFS endpoint assessment.

Figure 4-1: Statistical Consideration for Power and Sample Size

Primary Efficacy Decision Using Simon's MinMax Design Based on RR: P0 = 5% vs. P1 = 15% Power = 80%; α = 0.20	
First Stage Sample Size	18
Upper Limit for First Stage Rejection of Drug	0
Maximum Sample Size	28
Upper Limit for Second Stage Rejection of Drug	2
Secondary Efficacy Decision Based on 1-Year PFS Rate Endpoint at the End of Complete Enrolment; Total enrolment of 28 patients per arm Duration of enrolment: 30 months Additional follow-up time: None 1-year PFS Rate	
P0	20%
P1	50%
Power	95%
2-sided α	0.05

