- ii. Documentation of the qualifications, training and experience of the PI and other study staff
- iii. Eligibility of consented/enrolled patients
- iv. Informed consent document and process
- v. Verification that the local PI and staff are performing trial functions in accordance with protocol
- vi. Accuracy, completeness and timeliness of data
- vii. Accuracy and completeness of all source documentation
- viii. Response evaluation: verify that responses are identified according to the protocol definition of response for any response that is a major endpoint
- ix. Toxicity
- x. Appropriate reporting of all AEs and SAEs as required by GCP, the protocol, IRB regulations, sponsor's SOPs and other regulatory requirements

The monitor shall meet with RN/Coordinator assigned to the trial to:

provide an itemized review of the deficiencies to the RN/Coordinator and remove items from itemized review which are corrected during this meeting

review and document corrections; the RN/coordinator should indicate any remaining deficiencies and provide corrective action plan for resolution

prepare summary report for PI and Monitoring Committee to include summary of systematic deficiencies, significant protocol deviations, summary of remaining deficiencies and RN/coordinator corrective action plan, recommendations for data collection, protocol revision for clarity

The Monitor shall meet with the overall PI to discuss the report and document the PI's responses prior to submitting final report to the Monitoring Committee

The final Monitoring Committee review of audit report and PI response and PI summary of protocol to date will be included in the annual renewal submission.

Egregious data insufficiencies that may impact the scientific integrity of the trial are reported to the Medical Director and Clinical Trial Review Committee.

Please see the attached supplementary Emory University WINSHIP CANCER INSTITUTE data safety monitoring plan policy document for a complete detail of the monitoring plan.

9 Statistical methods and data analysis

All treated subjects will be included in the analysis of efficacy and safety.

Demographic and baseline characteristics will be summarized using descriptive statistics. The toxicities will be tabulated by organ system. Time to disease progression and overall survival will be evaluated using the Kaplan-Meier method.

Correlative analysis will be exploratory in the context of this Phase II screening trial.

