Between Arms: Any treatment arm closed to accrual after the first stage interim analysis will be considered an inferior arm and will be excluded from comparison for the winner of trials. The arm with the best overall RR at the end of full enrolment will be adjudged the winner to be considered for further development provided there are at least 3 objective responses. Only in the event of identical RR between 2 or more arms or if none of the arms met the RR criterion (less than 3 objective responses after full patient enrolment) would the 1-yr PFS rate be employed to determine a winner. Based on recent clinical trials of targeted agents in similar patient population, 90% of patients were alive at 1 year and median progression free survival ranged between 9 and 18 months.⁸⁻¹⁰ We assume a conservative estimate that only 20% of the patients will be progression free at 1 year if the treatment is ineffective while 50% or more of the patients will be progression free at the same time point with an effective regimen. For this purpose, a 1-year PFS rate of 50% or greater will be considered sufficient activity to justify further evaluation of the treatment in this disease. Assuming a 20% or lower 1-year PFS rate with an inactive regimen and a 50% or greater rate with an active regimen, 28 patients enrolled onto each arm will classify the treatment as having sufficient activity for further evaluation with a probability of 0.95 (power against the alternative hypothesis $p = 0.05$). In this respect, the arm with the highest 1-yr PFS rate will be judged the winner. In the event of a tie between the arms for both the RR and 1-yr PFS rate, the arm with the best profile in terms of safety and tolerability will be considered the overall winner to be selected for further evaluation in this disease. The power calculation for PFS assessment assumes full enrolment of 28 patients to the treatment arm, therefore any arm closed to further accrual following the initial interim analysis will not be eligible for the PFS endpoint assessment. The investigational agents in this trial have not been previously studied in thyroid cancer; therefore we are unable to accurately determine the drop-off rate. Nonetheless, all patients

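### The 1-year PFS rate is read at the end of a 30-month enrolment with no further follow-up, which costs precision; a data cut 6 to 12 months later is a cheap, minor improvement

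*Combined protocol and SAP*

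**What the plan says.** Section 3.1 lists PFS as a primary objective and section 7.4 lists it as a primary endpoint. Figure 4-1 in section 4 treats it as the second efficacy decision, a "1-Year PFS Rate Endpoint at the End of Complete Enrolment", planned for 28 patients per arm with "Duration of enrolment: 30 months Additional follow-up time: None". The other inputs are P0 = 20%, P1 = 50%, power 95% and two-sided alpha 0.05. Sections 4 and 9.1 say that "28 patients enrolled onto each arm will classify the treatment as having sufficient activity for further evaluation with a probability of 0.95". Neither names the test.

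Section 9 names one time-to-event method: "Time to disease progression and overall survival will be evaluated using the Kaplan-Meier method".

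Response rate comes first in choosing a winner: "The arm with the best overall RR at the end of full enrolment will be adjudged the winner". The 1-year PFS rate is used "Only in the event of identical RR between 2 or more arms or if none of the arms met the RR criterion" (fewer than 3 responses). Then "the arm with the highest 1-yr PFS rate will be judged the winner", and "a 1-year PFS rate of 50% or greater will be considered sufficient activity" to go on.

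Section 4.2 follows patients until they stop treatment and contacts them for survival until 30 days after the last patient's last visit. It neither dates that visit nor moves the PFS readout. No section requires 12 months of follow-up before the 1-year rate is read.

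**The concern.** A 12-month rate is best estimated when most patients have been observable for 12 months. At the stated cut, patients who entered in the last year have not been. The Kaplan-Meier estimate at month 12 then rests on a thin risk set: about 8 patients per arm if the true rate is 50%, against 14 with a further year of follow-up.

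What is at stake is the precision of a listed primary endpoint, which is also the tie-breaker between arms. The plan's 95% also cannot be interpreted without knowing which test it belongs to.

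**Working it through.** **Inputs.** From Figure 4-1: n = 28 per arm, accrual 30 months, added follow-up 0, P0 = 0.20, P1 = 0.50, two-sided alpha 0.05. Assumed, because the plan is silent: even accrual and exponential PFS. The monthly hazards are then λ0 = −ln(0.20)/12 = 0.1341 and λ1 = −ln(0.50)/12 = 0.0578.

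**1. Share with less than 12 months of potential follow-up.**
- Even accrual: 12/30 = 40%, and 0.40 × 28 = 11.2 patients per arm.
- Accrual falling linearly to zero: (12/30)² = 16%.
- Accrual rising linearly from zero: 1 − (18/30)² = 64%.

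**2. The plan's 95%.** In a constant-hazard test, the chance that a patient's progression is seen by the cut is 1 − (1 − e^(−30λ))/(30λ). This is 0.756 under P0 and 0.525 under P1, so the expected events are 28 × 0.756 = 21.2 and 28 × 0.525 = 14.7. On the log-hazard scale:

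power = Φ{[ln(λ0/λ1) − 1.96/√21.2] × √14.7} = Φ{[0.842 − 0.426] × 3.83} = Φ(1.60) = 94.5%.

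The plan's figure is therefore reproduced with its own timing. A normal approximation for a proportion, with all 28 patients' 12-month status known, gives 94.6%, so the figure alone does not show which test was meant.

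**3. Kaplan-Meier at month 12.** The large-sample variance is S(12)²/n × ∫ λ/[S(u)G(u)] du over 0 to 12 months, with G(u) = 1 − u/30 at zero follow-up. Relative to complete 12-month follow-up, the variance rises by a factor of 1.315 at 50% and 1.363 at 20%. The effective size at 50% is 28/1.315 = 21.3.

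- Standard errors: √(0.25/28 × 1.315) = 0.108 at 50%, and √(0.16/28 × 1.363) = 0.088 at 20%.
- Power with the null variance in the critical value: Φ[(0.30 − 1.96 × 0.088)/0.108] = 88%.
- The same on the complementary log-log scale: 84%.
- With the alternative variance only: 79% (plain scale) or 77% (log-log).

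Simulation used 40,000 arms per scenario and Greenwood variance:

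| Months after last entry | 0 | 6 | 12 |
|---|---|---|---|
| SD of the 12-month rate (true 50%) | 0.109 | 0.098 | 0.095 |
| Mean 95% half-width | 0.21 | 0.19 | 0.18 |
| Power, nominal limits | 79-80% | 87-89% | 91% |
| Power, calibrated to one-sided 0.025 | 83% | 91% | 91% |
| Power, formula with null variance | 84-88% | 90-93% | 92-95% |
| Power, constant-hazard test | 94.5% | 97.4% | 98.4% |

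With nominal limits and zero follow-up, power is 67% for rising accrual and 87-89% for falling accrual. If 5-20% of patients per year are censored for toxicity (an assumption), it is 73-79% at 0 months and 85-90% at 12 months.

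**4. Effect on the plan's decision.** The simulated chance that a 50% arm ranks first is about 96.5% against two 20% arms at the planned cut. It is about 98% at 6 months and 98.6% at 12 months. Against two 35% arms (an assumption) the figures are 74%, 78% and 79%.

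Under the Simon rule with independent arms, the PFS criterion is reached in 17-20% of trials when at least one arm has a true response rate of 15% and the others 5% or 15%. It is reached in 27% if all arms are at 10%, and in 57% if all are at 5%. In rough terms, the planned cut changes the winner in 0.17 × 2.2 = 0.4 to 0.20 × 5 = 1 percentage point of trials with an active arm. If all arms are at 5% it is up to 0.57 × 5 = 2.9 points. These products treat response and PFS as independent and always compare three arms, so they show only the order of size.

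**The case against.** The strongest reply is that the timing is already in the power calculation. The 30 months and the absence of follow-up stand beside P0, P1 and the power as planning inputs, and a constant-hazard test on them returns the stated figure. That stands. A reader might infer that the 95% is false; the documents do not support this.

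It can also be said that section 9 names Kaplan-Meier for evaluating time to progression, not as a test against 20%, so 79-88% judges the plan by a test it never adopts. That is fair. The low end also reflects conservative limits (one-sided error 0.015-0.020), and even 12 months of follow-up gives only 91% with them. Part of the distance to 95% is therefore the choice of test and not follow-up. What remains is that the plan names no other method, so the reader cannot tell which power applies.

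Third, the 40% rests on even accrual, and two-stage enrolment with possible arm closure could move it either way. That too stands, hence the 16-64% range.

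Finally, section 4.2 keeps patients on scheduled visits until they stop treatment, so later data would exist. True, but Figure 4-1 does not use them for this decision.

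**Conclusion.** The point holds as a minor one. The planned cut leaves about 40% of patients short of 12 months under even accrual. The standard deviation of the 12-month rate is about 0.109 instead of 0.098 (6 months later) or 0.095 (12 months later). Most of the gain comes in the first 6 months. The effect on picking the winner is small at the plan's own P0 and P1. The sizes assume even accrual and exponential PFS.

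Three stronger readings are tempting and should not be drawn:
- That the late entrants are lost, leaving 17 patients per arm. They contribute early events and censored time, and the effective size is about 21.
- That the 95% is an error. It is reproduced, but it depends on a test and an assumption the plan does not state.
- That the response-rate ranking is also premature because it is placed at the end of full enrolment. Sections 4, 7.4 and 9.2 count evaluable patients, which in section 7.4 means two completed cycles (unless the patient progresses earlier), and section 7.4 plans a central review of all responses at the end of the study.

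**What to change.** In Figure 4-1 and section 9.1, set the data cut for the 1-year PFS rate at least 6 and at most 12 months after the last patient is enrolled. Use the imaging already scheduled every two cycles.

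No extra patients are needed. The cost is a PFS readout 6 to 12 months later. Under even accrual, the patients short of month 12 and still progression-free at the present cut number 11.2 × (1 − p)/(12λ) per arm: 5.6 if the true rate p is 20% and 8.1 if it is 50%. Following them all to month 12 takes about 25 to 43 patient-months per arm. At one scan per 8 weeks (1.84 months) that is about 13 to 23 scans, plus visits and drug supply for those still on treatment. A 6-month cut needs less. Patients who stop for toxicity have contact but no scheduled imaging under section 4.2, and would be censored as now.

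If the cut must stay at the end of enrolment, add two sentences: one naming the test and the constant-hazard assumption behind the 95%, and one giving the Kaplan-Meier power beside it (about 79-88% under even accrual).

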4.1 Treatment

Everolimus (10mg) orally continuously day 1-28

Pasireotide LAR 60 mg i.m. day 1 of each cycle

Safety and efficacy will be assessed throughout the treatment period.

4.2 Follow-up

Patients will remain on treatment and be followed at regularly scheduled office visit until treatment discontinuation due to progression, withdrawal of consent, or intolerable toxicity. Patients who discontinued therapy for reason of toxicity will be monitored at least monthly via phone or office visit until resolution of the adverse event. "All patients will be contacted for survival follow-up at least monthly via phone or office visit until death or the completion of the trial (LPLV + 30 days).

[figure not shown]

Figure 4-2: Flow diagram of the study schema, screening, stratification and randomization to one of 3 arms.

5 Population

Ninety adult patients with pathologically confirmed medullary or differentiated thyroid cancer who no longer benefit from or are intolerant of radioiodine therapy will be enrolled in the study. Patients will be enrolled across all participating sites in order of registration into the study. Patients who meet the eligibility and screening requirement will be stratified by histology, for the purposes of randomization to one of the 3 treatment arms. Patients will be randomly assigned to one of three treatment arm as described in the statistics section for a total of thirty patients in each arm.

Inclusion/exclusion criteria

The investigator or his/her designee must ensure that all patients who are offered enrollment in the study meet all of the following inclusion and exclusion criteria:

5.1 Inclusion criteria

1. Histologic or cytologic confirmation of thyroid cancer (papillary, follicular, medullary); histologic variants such as Hurthle and tall cell variants are allowed.
2. Biochemical or radiologic documentation of disease progression within the last 12 months prior to enrollment.
3. Presence of at least one site of measurable disease according to RECIST criteria version 1.1
4. Patient must have radioiodine refractory disease as defined by one or more of the following conditions:
 - All cases of medullary thyroid carcinoma
 - No iodine-uptake on a post- radioactive iodine treatment scan (in presence of low iodine diet and thyroid stimulating hormone (TSH) suppression) in an anatomically defined lesion that qualifies as target lesion by RECIST criteria

OR

 - If there is demonstrable iodine-uptake: the last radioiodine therapy of (≥ 100 mCi) was given within the last 16 months OR if given more than 16 months before enrollment, there is evidence of disease progression after each of the last two radioiodine treatment performed within 16 months of each other (each dose should be ≥ 100 mCi)

OR

 - If the patient has received the maximum cumulative life time dose of radioactive iodine treatments of at least 600 mCi
 - If the patient declines or is intolerant of radioiodine therapy or if with progressive disease that is, in the opinion of the treating physician, likely to benefit from biologic therapy rather than further iodine therapy e.g. patient with heavy burden of disease
5. Age ≥ 18 years.
6. Minimum of four weeks since any major surgery or since completion of radiation (patients should have adequately recovered from the acute toxicities of any prior therapy).
7. ECOG performance status ≤ 2 .
8. Life expectancy of at least 6 months.
9. Adequate bone marrow function as shown by: ANC $\geq 1.5 \times 10^9/L$, Platelets $\geq 100 \times 10^9/L$, Hgb > 9 g/dL.
10. Adequate liver function as shown by: serum bilirubin ≤ 1.5 x upper limit of normal (ULN), and serum transaminases activity ≤ 3 x ULN,.
11. Adequate renal function as shown by serum creatinine ≤ 1.5 x ULN or GFR of 60cc/ml using the formula of Cockcroft and Gault.
12. Fasting serum cholesterol ≤ 300 mg/dL OR ≤ 7.75 mmol/L AND fasting triglycerides ≤ 2.5 x ULN. NOTE: In case one or both of these thresholds are exceeded, the patient can only be included after initiation of appropriate lipid lowering medication.
13. Women of childbearing potential must have a negative serum pregnancy test within 7 days of the administration of the first study treatment. Women must not be lactating. Both men and

women of childbearing potential must be advised of the importance of using effective birth control measures during the course of the study.

14. Signed informed consent to participate in the study must be obtained from patients after they have been fully informed of the nature and potential risks by the investigator (or his/her designee) with the aid of written information.
15. INR and PTT $\leq 1.5 \times$ ULN. (Anticoagulation is allowed if target INR ≤ 1.5 on a stable dose of warfarin or on a stable dose of LMW heparin for >2 weeks at time of randomization.)

